## Statistical Analyses

Assuming that there are no ordering or period effects in the trial, we will use a paired t-test to compare ratings of anxiety during the impromptu speech task after BHV-0223 vs. placebo treatment. Given a sample size of 20 subjects, assuming a one-sided  $\alpha=0.1$ , we would have 80% power to detect a treatment effect size=0.5 or greater. As a comparison previous studies of benzodiazepines have demonstrated an effect size of at least 0.9 on similar speech paradigms (32). Our primary measure will be the VAS-anxiety after the impromptu speech task (BHV-0223 compared to placebo). As additional secondary measures we will collect (1) subject ratings of speech performance, self-statements during public speaking (SSPS) and specific anxiety symptoms during speech (STAI); (2) clinical ratings of speech performance; (3) duration of speech; (4) assessments of cognition – (DSST and 15 word recall) and 5) side-effects.

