#### **7. Plan for reporting adverse events to co-investigators on the study, as appropriate the protocol's research monitor(s), and funding and regulatory agencies, and regulatory and decision-making bodies.**

For the current study, the following individuals, funding, and/or regulatory agencies will be notified (choose those that apply):

All Co-Investigators listed on the protocol.

Food and Drug Administration

The principal investigator ([name]) will conduct a review of all adverse events upon completion of every study subject. The principal investigator will evaluate the frequency and severity of the adverse events and determine if modifications to the protocol or consent form are required.

- d. For multi-site studies for which the Yale PI serves as the lead investigator: N/A
  - i. How will adverse events and unanticipated problems involving risks to subjects or others be reported, reviewed and managed?

- ii. What provisions are in place for management of interim results?
- iii. What will the multi-site process be for protocol modifications?

**12. Statistical Considerations:** Describe the statistical analyses that support the study design.

Assuming that there are no ordering or period effects in the trial, we will use a paired t-test to compare ratings of anxiety during the impromptu speech task after BHV-0223 vs. placebo treatment. Given a sample size of 20 subjects, assuming  $\alpha=0.05$ , we would have 80% power to detect a treatment effect size=0.58 or greater. As a comparison previous studies of benzodiazepines have demonstrated an effect size of at least 0.9 on similar speech paradigms (32). Our primary measure will be the VAS-anxiety after the impromptu speech task (BHV-0223 compared to placebo). As additional secondary measures we will collect (1) subject ratings of speech performance, self-statements during public speaking (SSPS) and specific anxiety symptoms during speech (STAI); (2) clinical ratings of speech performance; (3) duration of speech; (4) assessments of cognition – (DSST and 15 word recall) and 5) side-effects.

We additionally take an interim examination of the efficacy data at the trial after 10 subjects to evaluate the initial side-effects of the compound and to examine initial efficacy. We would consider a treatment effect size of less than 0 (BHV-0223 worsen anxiety during the impromptu speech task compared to placebo) as a rationale to stop the trial early.

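### Sections V.3 and V.12 give different significance levels and detectable effects for the same primary paired t-test on 20 subjects, so the primary alpha is not fixed

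*Combined protocol and SAP*

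**What the plan says.** The primary analysis is set out in two places in the combined protocol and SAP, in nearly the same words.

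- **Section V.3, Research Plan, under Statistical Analyses.** The test is given as "we will use a paired t-test to compare ratings of anxiety during the impromptu speech task after BHV-0223 vs. placebo treatment". The power sentence begins "Given a sample size of 20 subjects, assuming a one-sided" alpha of 0.1 and ends "we would have 80% power to detect a treatment effect size=0.5 or greater".
- **Section V.12, Statistical Considerations.** The test, the primary measure (VAS-anxiety after the speech task) and the 0.9 benzodiazepine comparison are repeated. The power sentence begins "Given a sample size of 20 subjects, assuming" an alpha of 0.05, names no side, and ends "we would have 80% power to detect a treatment effect size=0.58 or greater".

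Section V.12 alone adds an interim look: "We additionally take an interim examination of the efficacy data at the trial after 10 subjects".

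Neither version is marked as superseded, and no other part of the document says which governs. Both alphas appear as assumptions of a power calculation. Neither section separately states the level at which the primary result will be called positive.

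**The concern.** One primary test can have only one type I error rate. Here a reader finds 10% one-sided in one section and 5% with no side in another, and no other decision level to settle the matter. A one-sided p-value between 0.05 and 0.10 would support a positive conclusion at the V.3 level and a negative one at the V.12 level.

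The missing side in V.12 adds a third possibility. Many readers take an unqualified 0.05 as two-sided, and on that reading the section's own claim of 80% power at 0.58 fails.

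Timing is a secondary point. Efficacy data are to be examined after 10 subjects, and the data and safety monitoring plan (Section V.11) makes the principal investigator responsible for monitoring the data. If the alpha is settled after that look, it cannot be shown that the choice was independent of the results.

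**Working it through.** **Inputs.** n = 20 pairs, paired t-test, 80% power (both sections). V.3: alpha 0.10 one-sided, effect 0.5. V.12: alpha 0.05, side not stated, effect 0.58. Benchmark effect 0.9 (both sections). Assumption: the effect size d is the mean within-subject difference divided by the SD of those differences. The document does not define it, but both stated figures reproduce on this definition.

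**Method.** Degrees of freedom are 19. The test statistic follows a noncentral t distribution with noncentrality d × √20. For a one-sided test at level a:

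power(d) = P(T > t(1−a; 19)), with T noncentral t, 19 df, noncentrality d × √20.

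The smallest observed standardized difference that reaches significance is t(1−a; 19) / √20, with √20 = 4.472. For two-sided 0.05 the critical value is the 0.975 quantile.

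**Step 1: reproduce the plan's figures.**
- V.3: noncentrality 0.5 × 4.472 = 2.236, critical t 1.328, power **81.7%**. The effect at exactly 80% power is 0.485, so the stated 0.5 is sound.
- V.12 read as one-sided: noncentrality 0.58 × 4.472 = 2.594, critical t 1.729, power **80.4%**. The effect at exactly 80% power is 0.577, so the stated 0.58 is sound.
- V.12 read as two-sided: critical t 2.093, power at 0.58 is **69.2%**. The effect at 80% power is 0.660, so the stated figure does not reproduce.

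**Step 2: compare the three possible rules at n = 20.**

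| Rule | Critical t | Smallest significant observed d | Effect at 80% power | Power at 0.5 | Power at 0.58 | Power at 0.9 |
|---|---|---|---|---|---|---|
| One-sided 0.10 | 1.328 | 0.297 | 0.485 | 81.7% | 89.5% | 99.6% |
| One-sided 0.05 | 1.729 | 0.387 | 0.577 | 69.5% | 80.4% | 98.7% |
| Two-sided 0.05 | 2.093 | 0.468 | 0.660 | 56.4% | 69.2% | 96.8% |

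**Step 3: how often the two sections give opposite answers.** On the one-sided reading this is the difference between the powers in the first two rows, that is, the chance that the observed d falls between 0.297 and 0.387.
- True effect 0: 0.100 − 0.050 = **5.0%**
- True effect 0.35 (the maximum): **15.2%**
- True effect 0.5: 0.817 − 0.695 = **12.2%**
- True effect 0.9: 0.996 − 0.987 = **0.9%**

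A simulation of 400,000 trials gave 12.2% at 0.5 and 5.0% at 0.

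**Step 4: alternative reading, V.12 as two-sided 0.05.** The band of disagreement in favour of the drug is then 0.297 to 0.468. It holds 0.100 − 0.025 = 7.5% of trials under no effect and 25.3% at a true effect of 0.5, with a peak of 28.4% near 0.39. This counts the benefit direction only. It is the less likely reading, because it contradicts V.12's own 0.58.

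**The case against.** The best defence is that both alphas sit in power sentences. Two correct power statements can coexist for one sample size, and neither section says that significance will be declared at its alpha. Strictly, then, the document gives two planning scenarios and no decision rule. That is accurate, but it does not help the plan. With no other level stated, these two numbers are all a reader has for judging the primary result, and they disagree.

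A second argument is scale. Section VI.A.7 calls this a proof-of-concept study. With 20 subjects, the estimate and its interval may matter more than a threshold. Sample size, test, endpoint and patient exposure do not change, and at the 0.9 benchmark the sections almost never disagree. This limits the consequence. It also supports a lenient alpha as a legitimate choice, but it must still be a single alpha chosen in advance.

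A third argument is that the look after 10 subjects carries only a stopping consideration for an effect below zero. No success claim or choice of alpha is attached to it. That is right, and the interim look is a reason to settle the matter early rather than evidence that anyone would exploit the gap.

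**Conclusion.** The concern holds. Two current sections assign different significance levels and detectable effects to one primary test, and nothing says which applies. This is an inconsistency and not a calculation error: each figure is right for its own alpha, provided V.12 is one-sided.

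The false-positive rate in favour of the drug is therefore 10% or 5% depending on the section read, or 2.5% if V.12 is two-sided. The chance that the choice of section changes the primary conclusion is largest for modest true effects and small for an effect as large as the benchmark.

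The result rests on d being in SDs of the within-subject difference, on all 20 subjects supplying both ratings, and on using the stated alphas as decision levels because no others are given. It needs correcting before any efficacy data are examined.

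**What to change.** Before the look after 10 subjects and before any unblinding, choose one alpha and one side, and put the same sentence in V.3 and V.12 with the matching effect at 80% power for n = 20:

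- one-sided 0.10 with 0.49 (the stated 0.5 is acceptable);
- one-sided 0.05 with 0.58; or
- two-sided 0.05 with 0.66.

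State that this alpha is the level at which the primary result will be declared, and that the effect size is in SDs of the within-subject difference.

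The cost is wording in two sections. The stated detectable effect may become somewhat less favourable, and no extra patients are needed.

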## 4. Genetic Testing N/A

### A. Describe

- i. the types of future research to be conducted using the materials, specifying if immortalization of cell lines, whole exome or genome sequencing, genome wide association studies, or animal studies are planned
- ii. the plan for the collection of material or the conditions under which material will be received
- iii. the types of information about the donor/individual contributors that will be entered into a database
- iv. the methods to uphold confidentiality

B. What are the conditions or procedures for sharing of materials and/or distributing for future research projects?

C. Is widespread sharing of materials planned?

D. When and under what conditions will materials be stripped of all identifiers?

- E. Can donor-subjects withdraw their materials at any time, and/or withdraw the identifiers that connect them to their materials?
  - i. How will requests to withdraw materials be handled (e.g., material no longer identified: that is, anonymized) or material destroyed)?
- F. Describe the provisions for protection of participant privacy
- G. Describe the methods for the security of storage and sharing of materials

5. **Subject Population:** Provide a detailed description of the types of human subjects who will be recruited into this study.

20 subjects who meet DSM-5 criteria for Social Anxiety Disorder and have a baseline LSAS public speaking subscale score >6 will be recruited through the Yale Child Study Center. We have experience recruiting subjects with social anxiety disorder through a trial examining the effects of ketamine for social anxiety disorder.

6. **Subject classification:** Check off all classifications of subjects that will be specifically recruited for enrollment in the research project. Will subjects who may require additional safeguards or other considerations be enrolled in the study? If so, identify the population of subjects requiring special safeguards and provide a justification for their involvement.

- |  |   |  |
|--|---|--|
|  Children              |  Healthy                                      |  Fetal material, placenta, or dead fetus |
|  Non-English Speaking  |  Prisoners                                    |  Economically disadvantaged persons      |
|  Decisionally Impaired |  Employees                                    |  Pregnant women and/or fetuses           |
|  Yale Students         |  Females of childbearing potential |  |

NOTE: Is this research proposal designed to enroll children who are wards of the state as potential subjects?  Yes  No (If yes, see Instructions section VII #4 for further requirements)

7. **Inclusion/Exclusion Criteria:** What are the criteria used to determine subject inclusion or exclusion?

**PATIENTS WITH SOCIAL ANXIETY DISORDER:**

*Inclusion Criteria:*

- 1) Male or female (post-menopausal, surgically sterile, or negative pregnancy test at screening and agreement to utilize an established birth control, including complete abstinence, during the testing period) between the age of 18 and 65 yrs.
- 2) Meet DSM-5 criteria for social anxiety disorder by structured clinical interview (SCID) and have a LSAS public speaking subscale score >6.
- 3) Stable psychiatric medications. Patients must have had stable doses of all psychiatric medications for the month prior to treatment and have been on stable doses of SSRI and antidepressants for at least 1 month prior to study enrollment. As needed benzodiazepine use will be permitted as long as subjects refrain from using benzodiazepines for the 48 hours prior to the study.
- 4) Medically and neurologically healthy on the basis of physical examination, SMAC-20 (including LFT's, TFT's), VDRL, CBC w/ diff, urinalysis, urine toxicology, EKG, and medical history. Individuals with stable medical problems that do not have CNS effects or interfere with medications administered (e.g., oral hypoglycemics) may be included if their medications have not been adjusted in the month prior to entry;
- 5) Urine toxicology screen negative for drug of abuse.
- 6) Able to provide written informed consent according to the Yale Human Investigation Committee (HIC) guidelines.

**Exclusion Criteria:**

1. Positive pregnancy test
2. Breastfeeding females
3. History of substance abuse disorder (ETOH, cocaine, opiates, PCP) within the last 6 months or positive urine toxicology on screening (within the previous 6 months).
4. History of pervasive developmental disorder or psychotic disorder by DSM-IV-TR criteria.
5. Presence of dentures, braces, piercings at the time of dosing, or any physical findings in the mouth or tongue that, in the opinion of the Principal Investigator, would be likely to interfere with successful completion of the dosing procedure.
6. Subjects with a medical condition that might interfere with the physiological absorption and motility (*ie*, gastric bypass, duodenectomy) or gastric bands.
7. Subjects with any clinically significant abnormality or abnormal laboratory test results.
8. Subject has a current diagnosis of viral hepatitis (HBsAG or HVC) or a history of liver disease.
9. Subject has significant history of seizure disorder other than a single childhood febrile seizure (eg. Epilepsy)
10. Subjects using any drugs known to induce or inhibit CYP 1A2 metabolism (examples of inducers: rifampin, carbamazepine, etc.; examples of inhibitors: fluvoxamine, ciprofloxacin, fluoroquinolones, etc.) within 30 days prior to the first study drug administration.
11. Subject with a history of allergic reactions to riluzole or other related drugs.
12. Subject has a history of anaphylaxis, a documented hypersensitivity reaction, or a clinically important reaction to any drug.
13. Subject has received another investigational drug or device within the 30 days (90 days for biologics) prior to the first dosing or is currently participating in an investigational study involving no drug administration.
14. Subject with clinically significant electrocardiogram (ECG) abnormalities (QTcF >450 msec) or vital sign abnormalities (systolic blood pressure lower than 90 or over 140 mmHg, diastolic blood pressure lower than 50 or over 90 mmHg, or heart rate less than 50 or over 100 bpm) at Screening or Baseline (Day -1).
15. Any reason which, in the opinion of the Principal Investigator, would prevent the subject from participating in the study.

8. How will **eligibility** be determined, and by whom?

Screening: After an initial telephone contact to rule out obvious exclusions from the study protocol, potential participants will be scheduled for a screening visit at the Yale Child Study Center. A member of our research team will discuss all aspects of this research: its purpose, the procedures that will be performed, any/all risks of the procedures, possible benefits, and possible alternative treatments. All patients will also

be informed that the standard of care for patients with SAD who have failed the first line treatments [SSRI, SNRI (or alternative SSRI), and CBT] is a trial of a monoamine oxidase inhibitor (MAOI), not Riluzole (National Institute for Health and Care Excellence 2013). The research team will discuss the inclusion and exclusion criteria for the study. If patients are considered eligible according to study criteria and if they agree to enroll in the study, they will sign the consent forms and schedule a time to go to the CNRU for screening visit 2.

Screening visit 2 will occur on the CNRU (may be done directly after Screening Visit 1 if convenient for the participant), and medical assessments (physical exam, EKG, blood draw, and urinalysis), and a battery of psychiatric rating scales will be performed, as indicated in Table 1 (excluding the SCID which is done during screening visit 1). We will also contact the subject's primary care provider or treating provider to confirm their psychiatric history and SAD diagnosis after receiving a signed release form from the subject.

9. **Risks:** Describe the reasonably foreseeable risks, including risks to subject privacy, discomforts, or inconveniences associated with subjects participating in the research.

The risks in this study include:

- 1) drug side effects of riluzole
- 2) worsening of symptoms
- 3) blood sampling
- 4) ratings
- 5) unanticipated side effects

### **Drug side effects**

BHV-0223 (riluzole) is a member of the benzothiazole class of medications. Chemically, its molecular formula is  $C_8H_5F_3N_2OS$  and its molecular weight is 234.2. The efficacy of riluzole in the treatment of ALS was established in two, well-controlled studies. Patients randomized to treatment with riluzole showed longer delay to tracheostomy or death compared to those treated with placebo. The recommended dose of riluzole in the treatment of ALS is 50mg taken every 12 hours (at least an hour before, or two hours after, a meal to avoid food-related decreases in bioavailability). Riluzole's mechanism of action in the treatment of ALS is unknown but thought to be due to its blockade of glutamatergic neurotransmission.

The most commonly observed adverse reactions of riluzole, dosed at 100mg/day, in placebo-controlled trials were asthenia (19.2%), nausea (16.3%), dizziness (3.9%), decreased lung function (10.2%), diarrhea (2.9%), abdominal pain (5.1%), pneumonia, vomiting (4.2%), vertigo (1.9%), oral paresthesia, anorexia (3.2%), and somnolence (1.9%). In a study with approximately 4,000 patients given riluzole for ALS, three cases of neutropenia were reported within the first two months of treatment.

Rarely, jaundice is a side effect as well. Riluzole has also been found to cause elevations in serum aminotransferase even in patients without a history of liver disease. Experience with riluzole in 800 patients with ALS demonstrated that approximately 50% of riluzole treated patients experienced at least one ALT/SGPT level above the upper limit of normal, 8% had elevations >3x upper limit of normal (ULN), and 2% >5x ULN.

A single non-ALS patient with epilepsy treated with concomitant carbamazepine and Phenobarbital experienced marked, rapid elevations of liver enzyme with jaundice four months after starting riluzole that returned to normal seven weeks after treatment discontinuation.

Riluzole's effect on liver functioning warrants monitoring of serum LFT levels every month during the first 3 months of treatment, every 3 months during the remainder of the first year, and periodically thereafter (PDR). Serum LFT levels should be evaluated more frequently in patients who develop elevations. Maximum increases in serum ALT usually occurred within 3 months after the start of riluzole therapy and were usually transient when <5x ULN. In trials, if ALT levels were <5 x ULN, treatment continued and ALT levels usually returned to below 2X ULN within 2-6 months. Treatment in studies was discontinued if ALT levels exceeded 5x ULN.

Riluzole is contraindicated in patients with a history of severe hypersensitivity reactions to riluzole or any of the tablet components. Riluzole should be prescribed with caution in patients with current evidence or history of abnormal liver function. Baseline elevations of several LFTs (especially bilirubin) should preclude the use of riluzole. Riluzole should be used with caution in elderly patients whose hepatic or renal functions may be compromised due to age. Females and Japanese patients may possess a lower metabolic capacity to eliminate riluzole compared to males and Caucasian populations. BHV-0223 may have reduced overall drug burden on the liver as the sublingual formulation avoids first-pass metabolism.

Patients should be instructed to report any febrile illness to their physicians. Patients should also be warned about the potential for dizziness, vertigo, or somnolence and advised not to drive or operate machinery until they have gained sufficient experience on riluzole to gauge whether or not it effects their mental or motor abilities. Patients treated with riluzole should be discouraged from drinking excessive amounts of alcohol as it may increase the risk of serious hepatotoxicity.

### **Worsening of symptoms**

Since Riluzole or placebo is added to the patients' current medications, the risk of symptoms worsening in this study is not significantly greater in this clinical trial than it would be if the patient's medications were changed as part of standard clinical care. Furthermore, the acute effects of study medications should dissipate within 8 hours of taking the single dose of medication. The only additional risks in this study are potential adverse effects of riluzole.

### **Blood sampling**

As a result of their participation in these studies, subjects will have more blood drawn than would be the case in usual clinical practice. Approximately three (3) tablespoons of blood will be drawn during the study. Subjects will be instructed to refrain from donating blood or participating in research involving blood donation during the study and for the 8 weeks following the study. Blood sampling may cause pain, bruising and infection. Some subjects may faint during blood sampling.

